### **Study Objectives:**

- 1- Measure visual analogue scores every 8 hours for 72 hours after surgery. Pain scores will be recorded by patients in a pain diary (see appendix)
- 2- Measure opioid requirements for the first 3 days after surgery
- 3- Measure patient satisfaction with their pain management.
- 4- Measure the quality of recovery (QOR) at 24 and 72 hours. using the QOR-9 questionnaire.( see appendix)
- 5- Measure the quality of sleep in the first two nights after surgery using a sleep questionnaire ( see appendix)
- 6- Functional outcomes will be assessed at 3 months follow up during the office visit or through administration of the disability assessment of shoulder and hand questionnaire, range of motion of the wrist and fingers will be recorded. (see appendix)

This study tests the hypothesis that patients receiving continuous ICB will have lower pain scores, will use less opioids, will sleep better the first two nights after surgery and will be more satisfied with their pain control regimen after surgery.

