**Recruitment:**

Patients will be identified from the surgical schedule the day before surgery and will be contacted by one of the study investigators to scan for eligibility for enrollment. Study aims and procedures will be explained to patients. Patients will be consented the morning of their surgery by one of the study investigator or the research coordinator.

25 patients will be enrolled in each study group with a total of 50 patients. Patients will be randomized to one of two study groups.

Group A will be named SS group, group B will be named the continuous infraclavicular block (CICB) group.

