**Randomization:**

A computer generated randomization table will be used for patient allocation to one of the two study groups; The SS group, or the CICB group. Randomization will be done in blocks of 10 patients. Patients' assignments will be written in a sealed envelope that is only open after patient consent for the study.

The study will be unblinded. Patients, nurses in the recovery room, and the research coordinator will be aware of the nature of patient assignment. **Currently, most patients presenting with distal radius fracture at PPMC will receive a single shot brachial plexus block for intraoperative anesthesia. We offer the continuous block option to patients with history of chronic pain or previous adverse reactions to oral opioids. Also these practices may vary depending on surgeon and anesthesiologist preference. Access to analgesic medications will not be restricted by any means for both study groups because of the study procedures.**

**Statistical Analysis:** Statistical analyses will be preformed using STATA 13 statistical software, Dallas, TX. Demographic data will be analyzed using student's T test or fisher's exact test as appropriate. Repeated measurements (pain scores) will be analyzed by repeated measures ANOVA or ANOVA on ranks, with further paired comparisons at each time interval performed using the t-test or Mann-Whitney U-test as appropriate. Categorical data will be analyzed using X analysis or Fisher's exact test where

applicable. Normally distributed data will be presented as means  $\pm$  SE of the mean (SEM), non normally distributed data are presented as medians  $\pm$  quartiles (interquartile range) and categorical data will be presented as raw data and as frequencies. The  $\alpha$  level for all analyses was set as  $P<0.05$ .

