#### **Measurements:**

- 1- Visual analogue scores every 8 hours for 72 hours after surgery. Pain scores will be recorded by patients in a pain diary
- 2- Measure opioid requirements for the first 3 days after surgery
- 3- Measure patient satisfaction with their pain management.
- 4- Measure the quality of recovery at 24 and 72 hours
- 5- Measure the quality of sleep in the first two nights after surgery. sleep quality questionnaire is adapted from the insomnia severity index (6) and we added

another questions asking about the frequency of waking up at night because of pain after surgery (7, 8)

6- Functional outcomes will be assessed at 3 months follow up during the office visit or through administration of the quick disability assessment of shoulder and hand (DASH) questionnaire (9), range of motion of the wrist and fingers will be recorded.

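### The rank fallback for the repeated pain scores, ANOVA on ranks, does not validly test the arm difference in either of its two usual meanings, and the plan does not say which procedure it means

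*Combined protocol and SAP*

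**What the plan says.** Study Objectives, item 1, is to "Measure visual analogue scores every 8 hours for 72 hours after surgery", and Measurements repeats this schedule. The hypothesis in Study Objectives is that "patients receiving continuous ICB will have lower pain scores", which is a comparison between arms. Under Recruitment, "25 patients will be enrolled in each study group with a total of 50 patients".

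The Statistical Analysis paragraph, which sits within the Randomization section, gives the method for these scores: "repeated measures ANOVA or ANOVA on ranks, with further paired comparisons at each time interval performed using the t-test or Mann-Whitney U-test as appropriate". Mann-Whitney is a two-sample test, so the paired comparisons can only be comparisons between the arms at each time. Alpha is 0.05 for all analyses, and no adjustment for multiple tests is stated.

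The paragraph does not say which rank procedure is meant, whether it contains arm or arm-by-time, how correlation within a patient is handled, or what triggers the switch from ordinary ANOVA.

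**The concern.** The rank alternative is the overall analysis of pain whenever the scores are judged non-normal. The plan provides for non-normal data. A switch is plausible, because scores may cluster near zero while a block is working, but this is an inference: the documents give no distribution.

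An analyst who looks up ANOVA on ranks will usually find Kruskal-Wallis or Friedman. Kruskal-Wallis is for independent observations. Friedman compares the repeated occasions with one another and ignores the arm. The first could report a benefit of the continuous block that is only noise. The second could report a significant result that says nothing about the block.

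**Working it through.** **Inputs from the documents.** Two arms, 1:1, 25 each. Scores per patient: 72/8 = 9 (10 if a time-0 score is added; none is stated). Alpha 0.05, taken as two-sided because sidedness is not stated. Sample Size Calculation: 38 evaluable patients, 20% dropout.

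**The plan's own figure.** 38/(1 - 0.20) = 47.5, so 48, close to the planned 50. Conversely 50 x 0.80 = 40 evaluable, or 20 per arm. The point does not depend on the sample size.

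**Assumptions, because the documents give no figures.** Within-patient correlation 0.3, 0.5 or 0.7; a pain profile that changes over time; SD 1.4 or 2.0 points, or results in SD units. Simulations used 19, 20 or 25 per arm and mostly 1,500 to 4,000 runs per setting, some with scores floored at 0. With 3,000 runs the standard error of a 5% rate is sqrt(0.05 x 0.95/3000) = 0.004.

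**Reading 1: Kruskal-Wallis on all stacked scores.** Forty patients become 40 x 9 = 360 observations. With equal correlation r, the variance of an arm mean is understated by the factor 1 + (9 - 1)r. The approximate true error rate is 2 x Phi(-1.96/sqrt(1 + 8r)).

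| r | 1 + 8r | Approximate error | Simulated error, no arm effect |
|---|---|---|---|
| 0.3 | 3.4 | 0.29 | 0.18 to 0.23 |
| 0.5 | 5.0 | 0.38 | 0.26 to 0.37 |
| 0.7 | 6.6 | 0.45 | 0.33 to 0.40 |

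The simulated values are mostly below the formula because the shared time profile widens the pooled ranks without adding noise between arms. Without a time profile, at r = 0.5, the simulation gave 0.368 against 0.381. Correlation that decays with time (AR(1), 0.7) gave 0.259, and skewed scores at r = 0.5 gave 0.314.

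**Reading 2: Friedman.** With no time trend (25 per arm, r = 0.5) it rejected in 4.2% of runs with no arm difference, 4.7% with a difference of 1 SD and 5.1% with 3 SD. It does not respond to the arm. With a time trend and no arm effect it rejected in 100% of runs.

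**Reading 3: repeated measures ANOVA on rank-transformed scores.** The arm test rejected in 0.039 to 0.059 of null runs. Its power was 0.88 against 0.89 for ordinary repeated measures ANOVA (19 per arm, 0.8 SD, r = 0.5).

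The arm-by-time test is less secure. With no arm effect it held 0.043 to 0.055 under equal correlation but rose to 0.086 under AR(1) 0.7 without correction. With a constant arm difference and r = 0.5 it was falsely significant as follows, depending on the time profile and the floor:
- SD 1.4: 9% to 17% at 1 point, 20% to 54% at 2 points.
- SD 2.0: 6% to 8% at 1 point, 8% to 12.5% at 2 points.

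It is not always inflated: it was 0.051 with a 1 SD difference and no time trend, and 0.053 with 0.8 SD and a time trend.

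**Replacement: rank-sum test on each patient's mean.** With two arms this is the same comparison as Kruskal-Wallis on one mean per patient. Null rejection was 0.037 to 0.057. Power was 83% against 84% for the t-test on the same means (1 point, SD 1.4) and 52% against 55% (SD 2.0). In the 19-per-arm setting above it was 0.87 against 0.89 for ordinary repeated measures ANOVA.

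**The case against.** The best defence is that the phrase directly follows repeated measures ANOVA, in a sentence about repeated measurements, so it may mean the same model run on ranks. That model keeps the arm and uses the patient as the error unit, and its arm test is valid with almost no loss of power. This stands. A reader might infer that the fallback cannot test a group difference at all, or that no reading of it is valid; the documents do not support either, because they do not name Friedman, Kruskal-Wallis or stacking.

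The same sentence also plans a t-test or Mann-Whitney test between arms at each time, with one score per patient. That stands too: the arm comparison does not rest on the rank ANOVA alone. But these are nine follow-up tests without adjustment, with familywise error of 1 - 0.95^9 = 0.37 if independent. They do not replace one overall test. Their multiplicity is a separate matter.

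The false interaction is a weaker point than the other two. It arises from a constant difference only when a real arm difference exists, so it would misdescribe a benefit, not invent one, and the hypothesis names no time-by-arm effect. Nor is it always peculiar to ranks. On scores bounded at 0 and 10 with SD 1.4 and a constant underlying difference, ordinary ANOVA showed it in 9% (1 point) and 52% (2 points), against 11% and 35% for ranks. On unfloored scores ordinary ANOVA held 4-5% while ranks gave 17% and 54%.

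Finally, one could keep a rank model and simply define it, with arm, time and patient as unit. That would repair the arm test but leave the interaction test open to this problem.

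**Conclusion.** The concern holds in limited form. In its two usual meanings the named fallback does not validly test the hypothesis: Friedman omits the arm, and stacked Kruskal-Wallis has a type I error of about 0.2 to 0.4 against 0.05. The third reading gives a valid arm test with an arm-by-time test that can mislead. Since the plan does not choose between them, the validity of the main pain result would depend on which procedure the analyst picks. This is more than missing detail, because the ordinary meanings of the named method give a wrong test, and it should be changed before analysis.

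The absence of an arm term in Friedman and the neglect of clustering in the stacked test do not depend on any assumption. The sizes do: they rest on assumed correlations of 0.3 to 0.7, an assumed time profile and assumed SDs. The consequence arises only if the rank alternative is used.

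**What to change.** In the Statistical Analysis paragraph, replace the words naming ANOVA on ranks with a sentence such as: if normality of the pain scores is doubtful, the arms will be compared by one two-sided Wilcoxon rank-sum (or permutation) test on one summary per patient, the mean (or time-weighted average) of the recorded 0-72 h scores, with a Hodges-Lehmann difference and 95% CI. State the rule for the switch in the same place.

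The estimate is then in pain-score points, the same scale as the 1-point difference in Sample Size Calculation. The time course stays described by the scores at each interval.

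The cost is one sentence, about 1 to 3 percentage points of power in the settings above, and the loss of any rank-based time-by-group test. Because the summary uses recorded scores, the plan should also say how incomplete diaries enter it.

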### **Methods:**

**Study design:** prospective, randomized, unblinded study with a parallel design and an allocation ratio of 1 to 1 for the treatment groups.

**Inclusion Criteria:** Patients scheduled for open reduction and internal fixation of a distal

radius fracture with American Society of Anesthesiologists (ASA) physical status I -III, mentally competent and able to give consent for enrollment in the study.

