**Sample Size Calculation:** A power analysis done prior to enrollment showed that the number of patients needed to detect a 1-point change in pain score ( $p<0.05$  significance level) was thirty-eight patients. While a 1-point change in pain score may not be clinically significant, we wanted the study to have enough power to detect between a 1-2 point pain score difference. Assuming a dropout rate of 20%, we will enroll fifty patients. Sample size estimate followed a previously published study comparing single shot versus continuous popliteal block for pain control after ankle fracture (5).

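### Normally distributed data are to be shown as mean ± SEM (4.4 to 5 times smaller than the SD), and no between-group difference with a confidence interval is planned for any outcome

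*Combined protocol and SAP*

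**What the plan says.** The Statistical Analysis paragraph (under Randomization) gives three presentation rules.

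- Normal data: "Normally distributed data will be presented as means" with, after the ± sign, the standard error.
- Non-normal data: medians with quartiles. The two rules meet in one sentence: "SE of the mean (SEM), non normally distributed data are presented as medians".
- Categorical data: "categorical data will be presented as raw data and as frequencies".

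The analyses named are all tests: t-test, Mann-Whitney, ANOVA for repeated measures or its rank version, chi-square and Fisher's exact. One significance threshold of 0.05 covers them ("level for all analyses was set as"). I found no planned SD, effect estimate or confidence interval in any section.

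The Sample Size Calculation says the number needed to detect a 1-point difference "was thirty-eight patients". It also concedes: "While a 1-point change in pain score may not be clinically significant". It then gives a difference of 1 to 2 points as what the study should have power to detect. Recruitment states that "25 patients will be enrolled in each study group with a total of 50 patients".

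**The concern.** There are two separate weaknesses.

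**Choice of summary.** The SEM measures how precisely a mean is estimated. The IQR measures how much patients differ from one another. If one is used for normal variables and the other for non-normal variables, the apparent variability of a variable depends on which side of the normality decision it falls. The rule is not limited to outcomes, so normally distributed baseline variables are affected too.

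**No estimate with an interval.** This is the more important weakness. The sample size text recognises that a difference can be detectable without being clinically important. A test result cannot make that distinction: a significant result may come from a difference that is too small to matter, and a non-significant one may still be compatible with a difference that does. The gap is widest where rank tests are used, because their P values carry no effect in pain points.

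**Working it through.** **Inputs from the documents**
- 25 enrolled per group, 50 in total (Recruitment), allocated 1:1 (Study design).
- 38 patients needed, 20% dropout, target difference 1 to 2 points (Sample Size Calculation).
- Significance level 0.05 (Statistical Analysis). Sidedness is not stated; two-sided is assumed.
- Neither the SD nor the power is stated.

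**The plan's own figures**
- Dropout: 38/(1 − 0.20) = 47.5, rounded up to 48, which is close to the 50 planned. With 20% loss, 50 × 0.80 = 40 remain, or 20 per group. The 38 needed, read as a total, is 19 per group.
- The 38 itself cannot be reproduced without an SD and a power. Back-solving with 19 per group, a 1-point difference and an assumed 80% power: SD = 1 × √(19/2)/(1.960 + 0.842) = 3.082/2.802 = 1.10. At 90% power it would be 0.95.

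**SEM against SD.** SEM = SD/√n, so SD/SEM = √n.
- 25 per group: √25 = 5.00
- 20 per group: √20 = 4.47
- 19 per group: √19 = 4.36

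**SEM against IQR for the same normal variable.** At 25 per group, mean ± SEM spans 2/5 = 0.40 SD. The IQR spans 1.349 SD. The ratio is 1.349/0.40 = 3.4.

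**Precision of a difference in means.** Half-width = t(0.975, 2n − 2) × SD × √(2/n). At 20 per group this is 2.024 × √(2/20) × SD = 0.640 × SD. The SD is an assumption throughout, so a range is shown.

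| Assumed SD (points) | 19 per group | 20 per group | 25 per group |
|---|---|---|---|
| 1.1 | 0.72 | 0.70 | 0.63 |
| 1.5 | 0.99 | 0.96 | 0.85 |
| 2.0 | 1.32 | 1.28 | 1.14 |
| 2.5 | 1.65 | 1.60 | 1.42 |
| 3.0 | 1.97 | 1.92 | 1.71 |

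These apply to a simple two-group comparison at one time point, or of one average per patient. The half-width is also the smallest observed difference that reaches P<0.05.

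**What the P value leaves out (20 per group)**
- Observed difference 1 point, SD 1.1: 1 ± 0.70 gives 0.30 to 1.70. This is significant, yet compatible with effects well under 1 point.
- Observed difference 1 point, SD 2: 1 ± 1.28 gives −0.28 to 2.28. This is not significant, yet compatible with the whole 1-2 point range.
- Observed difference 0: the interval is ±0.70 at SD 1.1, which excludes 1 point, and ±1.28 at SD 2, which does not. The P value is the same in both cases.

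**The case against.** The strongest reply is that this is a matter of reporting style and that little information is lost. On the normal branch that is largely right. Given both means, both SEMs and the group sizes, a reader can recover SD = SEM × √n, and the standard error of the difference as √(SEM₁² + SEM₂²). With equal SEMs, the half-width is t × √2 × SEM = 2.011 × 1.414 = 2.84 SEM at 25 per group. But this needs the number of patients at each time point, and it does not help with medians and rank tests, where no effect in points can be recovered from the planned outputs.

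It is also fair to say that the 1-2 point range appears in the plan as a power target and not as a criterion for judging the result. The stated hypothesis is directional: lower pain scores. Reading the result against that range is a recommendation. It rests on the plan's own doubt about the importance of 1 point.

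Four stronger readings are tempting, and the documents do not support them.

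- A reader might infer that every outcome will be shown as mean ± SEM. The same sentence assigns medians with quartiles to non-normal data and frequencies to categorical data. Pain and opioid use may well be skewed and fall under the median rule.
- A reader might infer that reporting is restricted to P values. The text sets a significance threshold; it does not mention intervals, but it does not rule them out.
- A reader might infer a five-fold understatement throughout. That needs all 25 per group; at 19 to 20 it is 4.4 to 4.5.
- A reader might infer that the interval must be wider than the 1-point target. At 20 per group that requires an SD above 1/0.640 = 1.56. At the SD of about 1.1 implied by 38 in total with 80% power, the half-width is 0.70.

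**Conclusion.** The point holds as a reporting weakness that should be corrected. For normal data the planned measure of spread is 4.4 to 5 times smaller than the SD at 19 to 25 per group, and it is not comparable with the IQR used beside it. No between-group estimate or interval is planned for any outcome, although the plan itself separates a detectable pain difference from a clinically significant one.

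How much the missing interval matters depends on an SD that the documents do not give. At 20 per group the half-width runs from about 0.7 points (SD 1.1) through 1.3 (SD 2) to 1.9 (SD 3). Over much of that range a P value alone would not show whether a 1-2 point effect is supported or excluded. A reader might conclude that the trial cannot answer its question at all. That goes too far: where means, SEMs and group sizes are reported, the interval can be rebuilt, and the planned tests remain valid for their purpose.

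**What to change.** In the Statistical Analysis paragraph, replace the SEM rule with mean (SD), keep median (IQR) for non-normal data, and add:

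> Between-group differences will be reported with 95% CIs (difference in means for normally distributed data, Hodges-Lehmann shift for non-normal data, difference in proportions for categorical data). For pain, the difference at each 8-hour time point and for the 72-hour average will be interpreted against the 1-2 point range in the sample size section.

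The Hodges-Lehmann shift goes with the Mann-Whitney test and gives an effect in pain points on the rank branch. Eight-hourly scores over 72 hours give 72/8 = 9 time points, so the time-point intervals should be labelled as unadjusted.

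The cost is small: displayed variability will look larger, and there is slightly more analysis work. No extra patients, visits or data are needed, and the tests and the sample size stay as they are.

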**Study procedures:**

In our institution we usually advocate for regional anesthesia and intravenous sedation for the repair of open fracture of the distal radius. Patients will be approached and consented for the study by one of the study staff.

Once consented their group assignment will be revealed to the anesthesiologist assigned to the room who will be performing the block

Patients will be monitored during block performance with standard ASA monitors. All patients will receive 2 L of oxygen via a nasal cannula. Sedatives will be titrated to effect. Midazolam 1-2 mg, and fentanyl 50-100 mcg will be used for sedation.

Block time out will be preformed according to standard operating procedure.

All blocks will be done under ultrasound guidance. Sonosite S nerve machine will be used with a low frequency curvilinear (C5) US probe with 2-5 MHZ frequency. Both single shot and continuous ICB will be performed according to the SOP in our department. Ultrasound survey of the deltopectoral groove below the clavicle will take place. The axillary artery and the three cords (posterior, medial and lateral) of the brachial plexus will be identified in short axis view deeper to the pectoralis minor muscle.

=====

For single shot blocks: A 4 inch 21 gauge single shot (B-Braun) needle will be introduced in-plane towards the posterior cord of the brachial plexus and 1-2 mL of dextrose 5% (D5%) bolus will be used to verify correct placement of the needle in the vicinity of the posterior cord and adequate spread pattern to both lateral and medial cord. 20 ml of Ropivacaine 0.5% will be injected through the needle with intermittent aspiration after each 5 ml bolus injection.

For the continuous block: A 4 gauge 18 inch touhy needle ( B –Bruan) will be introduced towards the posterior cord as above. When the needle tip and the pattern of spread is confirmed using D5% solution, a 21 gauge catheter will be introduced 2 cm beyond the needle tip under ultrasound visualization. The needle will be withdrawn over the catheter. Injection of a total of 20 ml of ropivacaine 0.5% ( in divided 5 ml boluses with intermittent aspiration) will take place through the catheter while observing the spread of local anesthetic under ultrasound. The catheter hub will be affixed to the upper lateral chest with sterile occlusive dressings and an anchoring device.

Block success will be defined as a change in cutaneous sensation to touch with an alcohol pad in the posterior, medial and lateral cord distribution over the forearm and the hand within 30min after injection. Subjects with successful catheter placement per protocol and nerve block onset will be retained in the study. Subjects with a failed catheter insertion or misplaced catheter indicated by a lack of sensory changes will have their catheter replaced or will be single shot blocked and withdrawn from the study.

Intraoperative sedation will consist of intermittent boluses of midazolam (1-2 mg), fentanyl (50-100 mcg) and propofol infusion, titrates to sedation and patient comfort (25-50 mcg/kg/min).

All patients will receive prophylaxis for postoperative nausea and vomiting (PONV) during surgery. The protocol for prophylaxis against PONV includes administration of 4 mg of dexamethasone after induction of anesthesia and 4 mg of ondansetron 20 minutes before recovery from anesthesia. Dexamethasone is withheld if the patient has poorly controlled diabetes mellitus (DM). Uncontrolled DM will be defined as random blood glucose above 250 mg/dl

**Protocol for postoperative analgesia:** At the conclusion of surgery, the catheters will be connected to a pump that will infuse local anesthetic. Ropivacaine 0.2% at a basal rate of 5 ml/hour and a patient administered on demand bolus of 5 ml with lock out interval every 60 minutes. In the PACU, intermittent boluses of hydromorphone will be used as needed. Postoperative analgesia will follow the current oral prescription protocol. Drugs that are used for postoperative analgesia include oxycodone/acetaminophen (5/325 mg) one to two tablets every four to 6 hours as needed by the patient with oxycodone 5-10 mg oxycodone oral tablets every 4 hours as needed for break through pain.

Patients will be followed up daily by the acute pain service resident as per our routine clinical practice for follow up for ambulatory perineural catheters. Patients will take out the catheter themselves at home as per protocol.

**Sample Size Calculation:** A power analysis done prior to enrollment showed that the number of patients needed to detect a 1-point change in pain score ( $p<0.05$  significance level) was thirty-eight patients. While a 1-point change in pain score may not be clinically significant, we wanted the study to have enough power to detect between a 1-2 point pain score difference. Assuming a dropout rate of 20%, we will enroll fifty patients. Sample size estimate followed a previously published study comparing single shot versus continuous popliteal block for pain control after ankle fracture (5).

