#### **Study duration:**

We plan to begin enrollment in October 2015. The enrollment of all subjects is projected to be completed in October 2016 with data analysis to follow. The study is expected to be completed by January 2017. The length of participation for each subject will be three months total – 3 months as follow up data will be collected during the follow up office visits.

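### Continuous-block patients converted to single shot after a failed catheter are withdrawn after randomisation, with no matching rule for failed single shot blocks and no analysis population that keeps them

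*Combined protocol and SAP*

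**What the plan says.** - **Order of events.** Under Randomization, the assignment is "written in a sealed envelope that is only open after patient consent for the study". Under Study procedures: "Once consented their group assignment will be revealed to the anesthesiologist assigned to the room who will be performing the block". Allocation is thus fixed and known before any needle is placed.
- **Success criterion.** "Block success will be defined as a change in cutaneous sensation to touch with an alcohol pad" in all three cord distributions within 30 minutes of injection. The definition is not limited to one technique.
- **Retention.** "Subjects with successful catheter placement per protocol and nerve block onset will be retained in the study". This mentions catheters only.
- **Failure.** Patients with a failed or misplaced catheter "will have their catheter replaced or will be single shot blocked and withdrawn from the study". No criterion separates the two routes. Patients whose catheter is replaced are not said to leave.
- **SS arm.** No consequence is given for a failed single shot block. The nearest text, in the exclusion criteria, concerns patients who choose general anaesthesia or refuse the block.
- **Analysis.** Statistical Analysis lists tests. It names no intention-to-treat, modified or per-protocol population and has no rule for withdrawn patients.
- **Follow-up.** Study duration says: "The length of participation for each subject will be three months total". Nowhere is it said whether converted patients go on completing diaries and questionnaires; on the ordinary meaning of withdrawal, they do not.

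**The concern.** As written, the CICB arm is filtered for technical success at onset and no such filter is stated for the SS arm. The SS patients who would have been technical failures with a catheter stay in; their counterparts in the CICB arm go out. Who goes also depends on an open choice between replacement and conversion, made by someone who knows the arm.

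Two consequences follow, each under a condition:

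1. If a working catheter helps and converted patients gain nothing from it, leaving them out overstates the effect of *assigning* a catheter.
2. If difficult placement goes with worse pain whatever the block, removing those patients from one arm lowers the CICB mean with no true effect. This also biases the comparison for the protocol's own hypothesis, that "patients receiving continuous ICB will have lower pain scores", because comparable SS patients remain in their arm.

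If failure is unrelated to later pain, there is no bias under the null. The protocol does not say which situation holds, and it would not collect the data to find out. A 72-hour diary that was never kept cannot be recovered at analysis.

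**Working it through.** **The plan's own figure.** Sample Size Calculation gives 38 evaluable patients and 20% dropout: 38 / (1 − 0.20) = 47.5, so 48, which is close to the 50 enrolled (25 per arm). 50 × 0.80 = 40, at least 38. The enrolment figure is consistent, but the allowance replaces numbers, not comparability.

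**Inputs.** From the protocol: 25 per arm, 1-point design difference, significance level 0.05 (taken as two-sided). Assumed, because the protocol gives neither a failure rate nor a link between failure and pain: k = 1, 2, 3 or 5 CICB patients withdrawn after the replacement option (f = k/25 = 4%, 8%, 12%, 20%), and correlation r = 0 to 0.6 between a propensity to fail and pain.

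**Step 1: overstatement of the as-randomised effect.** If converted patients gain nothing, the as-randomised effect is (1 − f) times the effect in retained patients. The ratio 1/(1 − f) is 25/24 = 1.04, 25/23 = 1.09, 25/22 = 1.14 and 25/20 = 1.25.

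**Step 2: false-positive rate favouring CICB (nominal 2.5%).** Simulation with no true effect, normal outcome, 25 per arm. The k patients highest on the failure propensity are removed from CICB only, followed by a pooled t-test; 200,000 runs per cell.

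| r | k=1 | k=2 | k=3 | k=5 |
|---|---|---|---|---|
| 0 | 2.5% | 2.5% | 2.5% | 2.5% |
| 0.2 | 2.8% | 3.2% | 3.6% | 4.1% |
| 0.4 | 3.3% | 4.0% | 4.9% | 6.5% |
| 0.6 | 3.8% | 5.2% | 6.7% | 10.3% |

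Removing the same number by the same rule from both arms gives 2.5% to 3.1% (r = 0, 0.4, 0.6). Most of the inflation therefore comes from applying the rule to one arm.

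**Step 3: spurious shift in the CICB mean.** The retained mean equals the full-arm mean minus f × (excess pain of failures over retained patients). For an excess of 1 to 2 points:

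- k=1: 0.04 to 0.08 point
- k=2: 0.08 to 0.16
- k=3: 0.12 to 0.24
- k=5: 0.20 to 0.40

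These compare with the 1-point design difference. The upper ends go beyond the Step 2 range. At r = 0.6 the excess is 1.01 to 1.23 SD, which at the SD of 1.07 used in Step 4 is about 1.08 to 1.32 points. The shift is then about 0.05 (1.32 × 1/25) to 0.22 (1.08 × 5/25).

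**Step 4: power if everyone is kept.** The protocol states no SD or power. Reading 38 as a total (19 per arm) and assuming 80% power for 1 point, the noncentral t distribution gives an implied SD of 1.07. Noncentrality is the difference divided by SD × √(1/n₁ + 1/n₂). Kept as randomised, the difference is 1 − k/25 with 25 v 25. Withdrawn, it is 1 with 25 v 25 − k. There is no other dropout in the first two rows.

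| | k=1 | k=2 | k=3 | k=5 |
|---|---|---|---|---|
| Kept as randomised, 25 per arm | 87% | 85% | 81% | 74% |
| Withdrawn | 89% | 89% | 88% | 86% |
| Kept, 20 per arm (20% other dropout) | 79% | 75% | 72% | 63% |

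**The case against.** The text of the rule is not in dispute; the case against concerns how much it matters.

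- *Silence about the SS arm is not a statement that failed SS patients are kept.* True. If the same criterion were applied to both arms, the error rate would be close to nominal (2.5% to 3.1%). But no such rule is written, and a plan followed as written withdraws patients from one arm only.
- *The hypothesis is about patients receiving a continuous block, so the 1.04 to 1.25 factor reflects a different estimand.* This stands for the first consequence. It does not answer the second, which biases the received-treatment comparison too.
- *Conversion is decided around block placement, before any postoperative pain score, so it cannot respond to outcomes.* Correct, and it limits the mechanism: bias needs a link between technical failure and later pain. The protocol neither supplies nor excludes one.
- *The direction is assumed.* This also stands. With r of −0.2 to −0.4 the rate favouring CICB falls to 0.8–2.2%, so the bias would run against the catheter.
- *The sizes are modest when failures are few.* Agreed. With 1 or 2 withdrawn and r up to 0.4, the two-sided error is 5.0% to 5.7%; at r = 0.6 it is at most 6.5%. The replacement option may keep withdrawals rare, and 5 of 25 is an extreme. But if they are rare, keeping those patients costs almost nothing.
- *The 20% dropout allowance covers it.* "Assuming a dropout rate of 20%, we will enroll fifty patients" makes up numbers; it does not restore balance between arms.

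**Conclusion.** The concern holds. Converted catheter patients leave after randomisation from a known arm, by an unspecified choice, with no counterpart rule in the SS arm and no analysis population that brings them back. This conclusion is textual and needs no numerical assumption.

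The size is illustrative. With 1 or 2 withdrawals, the false-positive rate favouring CICB is 2.5% to 5.2% for r from 0 to 0.6; the 10.3% figure is the extreme corner (5 withdrawn, r = 0.6). The effect of assigning a catheter is overstated by 4% to 25% if converted patients gain nothing. With no link between failure and pain there is no bias under the null.

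The case for changing the rule rests on the broken comparison and the irrecoverable diaries in a small, open-label trial with patient-reported pain, not on the worst-case figures. The finding covers failure of placement and onset only; the rule does not reach later catheter problems.

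**What to change.** Under Study procedures, delete the withdrawal of converted patients and insert:

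*All randomised patients, including those whose catheter is replaced or who are converted to single shot, remain in follow-up, complete all diaries and questionnaires, and are analysed in the group to which they were randomised. Block success, by the definition above, is recorded for every patient and failures are reported by arm.*

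Repeat the as-randomised population under Statistical Analysis. A successful-block subset may be shown only as a labelled sensitivity analysis, using the same success rule in both arms. Clinical handling of a failed block is unchanged.

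**Cost.** A two-sentence amendment and a few extra diaries. The estimated effect may be smaller, and power is lower if failures are frequent (Step 4). If 38 was meant per arm, which the protocol leaves open, the same 80% assumption implies an SD of about 1.54, and as-randomised power with 25 per arm is only about 58%, 55%, 51% and 44% for 1, 2, 3 and 5 failures. Most of that shortfall comes from the sample size rather than from this change: on the same assumptions, power with no failures is about 62%.
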